7.3 Labelling

Labels will be prepared in accordance with Good Manufacturing Practice (GMP) and local regulatory guidelines. The labels will fulfil GMP Annex 13 requirements for labelling. Label text will be translated into local language.

7.4 Storage

All study drug should be kept in a secure place under appropriate storage conditions. The investigational product label specifies the appropriate storage.

7.5 Compliance

The administration of all study drugs (including investigational products) should be recorded in the appropriate sections of the Case Report Form.

7.6 Accountability

The study drug provided for this study will be used only as directed in the Clinical Study Protocol.

IP kits will have the unique number identifiers and will be assigned through the Correction Phase and subsequent the Maintenance Phase. On receipt of IP supplies the Investigator/designee will check the supplies against the shipment manifest and will confirm receipt of IP shipments via the IVRS/IWRS. The system will then issue an acknowledgement

receipt. Sites are required to place all shipment manifests and acknowledgement receipts in the site regulatory binder.

Study drug will not be distributed to the study site until the contract is concluded between the study site and AstraZeneca. The Investigational Product Storage Manager is responsible for managing the study drug from receipt by the study site until the return of all unused study drug to AstraZeneca. AstraZeneca will provide the study documents 'Procedures for drug accountability' and 'Procedures for drug storage' which describes the specific requirements. The Investigator(s) is responsible for ensuring that the subject has returned all unused study drug.

7.7 Concomitant and other treatments

All concomitant medications taken by the patient from 7 days prior to the Correction Phase Day 1 until Maintenance Phase EOS visit, or the end of the study (7 ± 1 days after the last dose of IP) for patients, will be recorded (including the reasons for increase/decrease/initiation/discontinuation of RAASi doses after Correction Phase Day 1).

It is expected that patients with diabetes will be enrolled. Use of insulin/insulin analog is not restricted however whenever possible, all blood draws collected for the study evaluation prior to meals during the study treatment period should be collected prior to any insulin/insulin analog treatment.

During the study, the patient must not receive alternative treatment for hyperkalemia (including medication). If dosing with IP is discontinued or the patient has completed dosing, the patient may receive alternative treatment for hyperkalemia if clinically indicated prior to completing the EOS visit scheduled 7 days after the last dose. Any alternative treatment administered during the above period must be recorded in eCRF.

In addition to therapies for hyperkalemia also other drugs with World Health Organization Anatomic Therapeutic Chemical classification code V03AE, i.e. potassium or ion binders such as sevelamer, calcium acetate, and lanthanum carbonate, are prohibited to be taken while receiving IP, as the effects of potassium binding drugs may effect safety laboratory assessments.

Any time a RAAS inhibitor or diuretic dose is adjusted or initiated during the Maintenance Phase, the subject will return to the site $7 (\pm 2)$ days later for a potassium measurement and recording of adverse events and concomitant medications (Subjects will arrive at the clinic in the morning after fasting for at least 8 hours prior to potassium sample collection.). If required the dose of ZS will adjusted or stopped based on the rules in this protocol.

7.7.1 Oral medications with gastric pH-dependent bioavailability

When co-administered with ZS, some oral medications with gastric pH-dependent bioavailability may exhibit a clinically meaningful increase or decrease in their bioavailability. Therefore, these drugs should be administered at least 2 hours before or 2 hours after ZS to mitigate the risk of drug interactions.

Drugs that should be taken 2 hours before or after ZS to avoid a possible raised gastric pH drug interaction are listed below:

Class of Drug	Drugs
Azole antifungals	Ketoconazole, Itraconazole, Posaconazole, Voriconazole
Anti-HIV drugs	Atazanavir, Nelfinavir, Indinavir, Ritonavir, Saquinavir, Raltegravir, Ledipasvir, Rilpivirine
Tyrosine kinase inhibitors	Erlotinib, Dasatinib, Nilotinib

7.8 Post Study Access to Study Treatment (Not Applicable)

8. STATISTICAL ANALYSES BY ASTRAZENECA

8.1 Statistical considerations

Analyses will be performed by AstraZeneca or its representatives.

A comprehensive Statistical Analysis Plan (SAP) will be prepared prior to first patient dosed and any subsequent amendments will be documented, with final amendments completed prior to database lock.

8.2 Sample size estimate

The sample size is estimated so that sufficient safety data of at least 100 Japanese subjects treated by ZS for at least one year can be generated, as required by ICH E1 guideline. Assuming approximately 35% drop out rate, approximately 150 subjects would be enrolled to this open-label study.

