5.10 Volume of blood	Table 5 Number of Samples and Maximum blood volume Total (mL) were updated. Added Visit 6 in footnote 1.	To align with Table 2 changes

Version 1.0, 9 March 2017
Initial creation

Clinical Study Protocol
Drug Substance ZS
Study Code D9482C00001
Version 5.0
Date 13 Sep 2018

This Clinical Study Protocol has been subject to a peer review according to AstraZeneca Standard procedures. The Clinical Study Protocol is publicly registered and the results are disclosed and/or published according to the AstraZeneca Global Policy on Bioethics and in compliance with prevailing laws and regulations.

CLINICAL STUDY PROTOCOL SYNOPSIS

A Phase 3 Multicenter Open-label Maintenance Study to Investigate the Long-term Safety of ZS (Sodium Zirconium Cyclosilicate) in Japanese Subjects With Hyperkalemia

Principal Investigator(s)

See Addendum.

Study site(s) and number of patients planned

This study will be conducted in approximately 30 centers in Japan. The primary objective of this Japanese study is to assess the safety and tolerability of long-term treatment of ZS flexible dose regimen (initial dose 5g once daily [QD] then up- or down- titrated based on the potassium level) for 12 months. In total 150 subjects will be entered into the Correction Phase to have approximately 100 subjects treated for 1 year, assuming a drop-out rate of around 35%.

Study period	Phase of development	
Estimated date of first patient enrolled	Q2 2017	Phase III
Estimated date of last patient completed	Q3 2019	

Study design

The study is an open label, single arm study with flexible dose regimen focused on assessing long-term safety and tolerability of ZS in Japanese subjects with hyperkalemia.

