Safety endpoints will include adverse events (including incidence of oedema-related events), vital signs, and other relevant clinical chemistry (specifically, the incidence of hypokalemia, hypomagnesemia, hypophosphatemia, and hypocalcemia), hematology, and urinalysis parameters. Kidney function will be evaluated by assessments of creatinine, estimated Glomerular Filtration Rate (eGFR), urine protein-to-creatinine ratio (UPCR) and urine albumin-to-creatinine ratio (UACR) over time. Liver function will be evaluated by assessing bilirubin, AST and ALT.

Clinical Study Protocol Synopsis
Drug Substance ZS
Study Code D9482C00001
Version 5.0
Date 13 Sep 2018

Sample size of in total 150 subjects to be enrolled to this study was determined so that at least safety data of 100 subjects treated by ZS as long as one year will be collected, assuming 35% drop out rate.

	PAGE
TITLE PAGE.....	1
VERSION HISTORY	2
CLINICAL STUDY PROTOCOL SYNOPSIS	8
TABLE OF CONTENTS	14
LIST OF ABBREVIATIONS AND DEFINITION OF TERMS.....	19
1. INTRODUCTION	21
1.1 Background and rationale for conducting this study	21
1.2 Rationale for study design, doses and control groups.....	24
1.3 Benefit/risk and ethical assessment	25
1.3.1 Clinical benefits	25
1.3.2 Clinical risks	26
1.3.3 Clinical benefit-risk balance	26
1.3.4 Conclusions	27
1.4 Study Design.....	27
2. STUDY OBJECTIVES	30
2.1 Primary objective	30
2.2 Secondary objectives.....	30
2.3 Exploratory objectives	31
3. PATIENT SELECTION, ENROLMENT, RESTRICTIONS, DISCONTINUATION AND WITHDRAWAL.....	31
3.1 Inclusion criteria	32
3.2 Exclusion criteria	32
3.3 Patient enrolment	33
3.4 Procedures for handling incorrectly enrolled	34
3.5 Methods for assigning treatment groups (Not Applicable).....	34
3.6 Methods for ensuring blinding (Not Applicable)	34
3.7 Methods for unblinding (Not Applicable).....	34
3.8 Restrictions	34
3.9 Discontinuation of investigational product	34
3.9.1 Procedures for discontinuation of a subject from investigational product.....	36
3.10 Criteria for withdrawal	36

3.10.1	Screen failures	36
3.10.2	Withdrawal of the informed consent.....	36
3.11	Interruption of investigational product.....	37
3.12	Discontinuation of the study.....	37
4.	STUDY PLAN AND TIMING OF PROCEDURES.....	38
4.1	Screening/Enrolment period (Visit 1)	42
4.2	Treatment period.....	42
4.2.1	Correction Phase Day 1 (Visit 2).....	42
4.2.2	Correction Phase Day 2 (Visit 3).....	44
4.2.3	Correction Phase Day 3 (Visit 4).....	45

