3.3 Patient enrolment

Investigator(s) should keep a record, the patient screening log, of patients who entered pre-study screening.

The Investigator(s) will:

1. Obtain signed informed consent from the potential patient or their guardian/legal representative before any study specific procedures are performed. Patient is considered enrolled in the study after she/he has signed the informed consent form (ICF).
2. Assign potential patient a unique enrolment number via Interactive Voice Response System (IVRS) / Interactive Web Response System (IWRS), beginning with 'E#'. .
3. Patients will remain associated with the same enrolment number throughout the entire study, and patients should NOT receive any new E-code if re-screened. If a patient signs the ICF but does not meet the inclusion/exclusion criteria the patient will be marked as a screen failure on the Screening and Enrolment Log provided by the Sponsor and will be entered in the Web Based Data Capture (WBDC) as a screen failure. Patients can be re-screened once. A new ICF does not need to be signed before re-screening if the original ICF was signed within 30 days and the ICF has not been revised.

If a patient withdraws from participation in the study, then his/her enrolment code cannot be reused.

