3.10.2 Withdrawal of the informed consent

Patients are free to withdraw from the study at any time (investigational product and assessments), without prejudice to further treatment.

A patient who withdraws consent will always be asked about the reason(s) and the presence of any adverse events. The Investigator will follow up AEs outside of the clinical study.

If a patient withdraws from participation in the study, then his/her enrolment code cannot be reused. Withdrawn patients will not be replaced.

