Urine HCG																			X ⁴
IP Reconciliation	X	X	X	X	X	X	X	X	X	X	X	X	X	X	X	X	X	X	X
Patient questionnaire																			X

- All blood potassium samples are analyzed by i-STAT and by the Central Laboratories on all occasions. Serum clinical chemistry, including S-K, hematology and urinalysis will be measured fasting and before administration of ZS. For diabetic patients all blood potassium samples should be collected prior to insulin administration whenever possible.
- Please see Table 6 for details on how to adjust the dose based on the measured potassium values.
- Maintenance Phase Study Day 1 sample will be the same sample as obtained on the last day of the Correction Phase.
- U-HCG will be performed exclusively for women of childbearing potential. Samples will be analysed locally, and the data will not need to be collected in the database. Pregnancies are instead reported on the dedicated Case Report Form (CRF) page.
- During the 12 months Maintenance Phase, the scheduled visit may take place either up to 2 days early or late by Visit 10 and up to 3 days early or late from Visit 11.
- EOS occurs 7±1 day after the last administration of IP
- Access IVRS/IWRS on visit indicated or if patient permanently discontinues dosing before the end of Maintenance phase.
- Central laboratory potassium sample collected as part of the serum chemistry panel.

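### About 150 subjects at about 35% drop-out give an expected 97.5 one-year completers, not at least 100, and the protocol words both the target and the denominator in two ways

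*Protocol*

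**What the plan says.** The protocol gives the sample size in three places.

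- **Section 8.2** sets the target as safety data from "at least 100 Japanese subjects treated by ZS for at least one year can be generated, as required by ICH E1 guideline", and then: "Assuming approximately 35% drop out rate, approximately 150 subjects would be enrolled to this open-label study".
- **Synopsis, statistical methods**, repeats the floor: "at least safety data of 100 subjects treated by ZS as long as one year will be collected, assuming 35% drop out rate".
- **Synopsis, number of patients planned**, is softer on the target and uses another denominator: "In total 150 subjects will be entered into the Correction Phase to have approximately 100 subjects treated for 1 year", with drop-out put at around 35%.

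Three other places bear on the figure.

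- Section 3.3 defines enrolment by consent: "Patient is considered enrolled in the study after she/he has signed the informed consent form (ICF").
- Section 3.10.2 says: "Withdrawn patients will not be replaced".
- The last maintenance visit is Visit 23 on Day 362. A footnote to Table 2 allows visits "up to 2 days early or late by Visit 10 and up to 3 days early or late from Visit 11".

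Section 8.5.1 rules out formal testing, so this exposure count is the whole basis for the number of subjects.

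**The concern.** A floor of 100 is claimed from inputs whose expected yield lies below 100. Section 8.2 ties that floor to a regulatory guideline, so a reader will take it as a commitment that the design has been sized to meet.

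Two wording conflicts make the claim harder to check. One Synopsis paragraph gives the target as approximate, while the other two places give it as a minimum. The 150 is counted at consent if Section 8.2 is read with Section 3.3, but at entry to the Correction Phase in the Synopsis.

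At stake is whether the stated justification agrees with its own inputs, and how the 100 will be tallied at the end. No estimate, test or error rate depends on it.

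**Working it through.** **Inputs.** Target T = 100 (Section 8.2 and Synopsis). Drop-out d = 0.35, given as approximate in Section 8.2 and in the Synopsis opening, and without qualification in the Synopsis statistical methods. N = 150, given as approximate in Section 8.2.

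**Reproducing the plan's figure.** The usual inflation is T / (1 − d) = 100 / 0.65 = 153.8, rounded up to 154. The plan has about 150, which is 4 fewer (4 / 154 = 2.6%). The common slip of multiplying, 100 × 1.35 = 135, does not give 150. The method was therefore sound and the result was rounded down.

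**Expected yield.** N × (1 − d) = 150 × 0.65 = 97.5, which is 2.5 below the floor. For an expected 100 from 150, drop-out may be at most 1 − 100/150 = 33.3%.

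**Chance of at least 100.** Let X be the number of completers, binomial with N = 150 and success probability 1 − d. This treats subjects as independent and d as known. The exact upper tail P(X ≥ 100) is:

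| Drop-out | Expected completers | P(at least 100) |
|---|---|---|
| 30% | 105 | 0.84 |
| 32% | 102 | 0.67 |
| 33.3% | 100 | 0.54 |
| 34% | 99 | 0.47 |
| 35% | 97.5 | 0.37 |
| 36% | 96 | 0.28 |
| 40% | 90 | 0.06 |

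With N = 154 at 35%, the expected number is 154 × 0.65 = 100.1 and the chance is 0.54.

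**Denominator.** Section 8.2 read with Section 3.3 counts consented subjects, screen failures included. The Synopsis counts entry to the Correction Phase. Section 7.2 divides subjects into a first 75 and a remaining 75 for the lower-dose scheme. That sums to 150 and concerns treated subjects, so it fits the Synopsis count.

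**Length of exposure.** The last dose falls on Maintenance Day 361 or 362, depending on whether a dose is taken at Visit 23. The Correction Phase adds 1 to 3 days.

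- Visit 23 on Day 362: 361 + (1 to 3) = 362 to 364 days, or 362 + (1 to 3) = 363 to 365 days.
- Visit 23 three days early: 359 to 361, or 360 to 362 days.
- Visit 23 three days late: 365 to 367, or 366 to 368 days.

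The protocol does not define one year in days. Section 7.2 speaks of up to 12 months and puts the end of treatment at Week 52 (52 × 7 = 364 days).

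**The case against.** The strongest reply is that this is ordinary rounding. Section 8.2 qualifies both the 35% and the 150 as approximate, and the Synopsis opening says approximately 100. The properly inflated number differs by only 4 subjects. The no-replacement sentence concerns withdrawn patients and does not cap recruitment. The 37% takes an approximate planning rate literally, and a rate a few points lower makes success more likely than not. The protocol sets no assurance level.

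Most of this stands, and it rules out a reading that some might infer: that the design fails its purpose. It does not remove the point. The rounding went below a stated minimum, and an approximate 35% can err upwards as well, with a chance of 0.28 at 36%.

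Two other strong readings are tempting and are not supported.

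- **That the 150 are consented subjects, so the yield is far lower.** The Synopsis and the 75 + 75 split in Section 7.2 point to treated subjects, and Section 3.10.1 keeps screen failures out of the study. No screen-failure rate is given from which to size a loss. What remains is a word in Section 8.2 that conflicts with the definition in Section 3.3.
- **That dosing must end short of 365 days.** The Visit 23 procedures in Section 4.2.11 list no dose, but that is silence rather than a statement, and the columns of the Table 2 dosing row have run together in the text at hand. With a dose on Day 362 after a full 72-hour Correction Phase, exposure is exactly 365 days, and a late Visit 23 gives more. The on-schedule gap is 0 to 3 days and matters only under a definition of one year that the protocol does not adopt.

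**Conclusion.** The concern holds as an inconsistency between the stated floor and the stated inputs. At 35% drop-out, 150 subjects fall 2.5 short of 100 in expectation. The 37% chance rests on exactly 35% independent drop-out from exactly 150 treated subjects; 97.5 needs only the two planning figures. The inputs support the approximate target in the Synopsis opening and not the minimum in Section 8.2 and the Synopsis statistical methods.

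The conflict over who is counted in the 150 is real but is one of wording, since the rest of the protocol indicates treated subjects. The meaning of one year is a minor clarification and not an established error.

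**What to change.** Amend the wording, without adding patients.

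1. In Section 8.2 and both Synopsis paragraphs, state that 150 subjects entering the Correction Phase are expected to give about 97 one-year completers at 35% drop-out, and that at least 100 are expected only if drop-out is about 33% or less.
2. Use one form of the target throughout. With the present inputs that form is *approximately 100*.
3. In Section 8.2, replace *enrolled* by *entered into the Correction Phase*, so that it agrees with the Synopsis and no longer conflicts with Section 3.3.
4. State which exposure counts as one year when the 100 are tallied, for example completion of Visit 23 (Day 362 ± 3).

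The cost is a few sentences, and a headline figure slightly less favourable than the one now printed. If the sponsor wants to keep *at least 100* as an expectation at 35% drop-out, the number to state is 154 treated subjects.

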8.3 Definitions of analysis sets

Analysis sets will be defined for each of correction phase and maintenance treatment phase.

8.3.1 Full analysis sets

All efficacy analyses will be performed using an Intent-to-Treat (ITT) principle based on the full analysis sets.

For the correction phase, the full analysis set will include all patients that receive the correction phase ZS dose and have any post-baseline correction phase S-K values.

For the subsequent long-term maintenance phase, the full analysis set will include all patients who receive ZS dose during maintenance phase and have any post-baseline maintenance phase S-K values.

8.3.2 Safety analysis sets

For the correction phase, the safety analysis set will include all patients as treated with at least one dose of correction phase ZS and had any correction phase safety data.

For the subsequent long-term maintenance phase, the safety analysis set will include all patients as treated with at least one dose of maintenance phase ZS and had any maintenance phase safety data.

8.4 Outcome measures for analyses

8.4.1 Efficacy variables (Secondary)

Maintenance phase

- Proportion of patients who can maintain normokalemia (defined as S-K level of ≥ 3.5 and ≤ 5.0 mmol/L, inclusive) on ZS at each Maintenance Phase study visit
- Proportion of patients with average S-K ≤ 5.1 mmol/L
- Proportion of patients with average S-K ≤ 5.5 mmol/L
- Proportions of patients who were normokalemic (S-K ≥ 3.5 and ≤ 5.0 mmol/L), hypokalemic (< 3.5 mmol/L), or hyperkalemic (> 5.0 mmol/L) at each Maintenance Phase visit.
- Subject-level average S-K over certain period of time
- Observed values at visit and change from baseline in S-K over time
- Number of normokalemic days during Maintenance Phase
- Change in S-K level from the last on-treatment Maintenance Phase visit to the End of Study
- Change from baseline in S-Aldosterone over time
- Proportion of patients with normal S-Aldosterone
- Change from baseline in S-Bicarbonate
- Proportion of patients with normal S-Bicarbonate
- SF-36 v2 questionnaire

Correction phase

- Observed values and change from Correction Phase baseline in S-K

- Proportion of patients who achieved normokalemia at 24, 48 and 72 hours after start of dosing
- Safety and tolerability as measured by adverse events reporting, vital signs, ECGs, physical examinations, and safety laboratory measurements during Correction Phase

8.4.2 Efficacy variables (Exploratory)

- Patient questionnaire on preference for low intensity ZS dosing(QOD or QD)
- Proportion of subjects increased RAASi doses
- Proportion of subjects who decrease or discontinued RAASi doses
- Proportion of subjects who increased at least once RAASi due to each reason
- Proportion of subjects who decreased/discontinued at least once RAASi due to each reason
- Time to first reduction/discontinuation of RAASi

8.4.3 Safety Variables

In this study, the following safety data will be collected: adverse events reporting, vital signs, ECGs, physical examinations, and safety laboratory measurements.

8.5 Methods for statistical analyses

8.5.1 Analyses of efficacy variables

Efficacy analyses will be performed separately for the correction phase and maintenance phase.

For continuous variables, the values at visit and change from baseline (and percent change from baseline, if appropriate) will be summarized by descriptive statistics. For categorical variables frequency and percentage will be summarized. Model-based point estimates and 95% CIs will also be presented if appropriate. Time to event (such as RAASi reduction) will be displayed with Kaplan-Meier plot. No formal statistical testing will be performed in this study.

8.5.2 Analysis of Safety data

Safety analyses will be performed separately for the correction phase and maintenance phase. Safety endpoints will include adverse events (including incidence of Oedema related events, defined as Fluid overload, Fluid retention, Generalised oedema, Hypervolaemia, Localised oedema, Oedema, Oedema peripheral and Peripheral swelling), vital signs, and other relevant clinical chemistry (specifically, the incidence of hypokalemia, hypomagnesemia, hypophosphatemia, and hypocalcemia), hematology, and urinalysis parameters. Kidney function will be evaluated by assessments of creatinine, eGFR, urine protein-to-creatinine ratio (UPCR) and urine albumin-to-creatinine ratio (UACR) over time. Liver function will be evaluated by assessing bilirubin, AST and ALT.

Treatment emergent AEs (TEAE) will be mainly analyzed. Adverse events will be classified by the Medical Dictionary for Regulatory Activities (MedDRA) to be consistent with other ZS studies. Safety data will be collected and analyzed while on study phases and reported until treatment-emergent adverse events are resolved. Unresolved adverse event outcomes at the end of treatment will be followed for an additional 7 days or until resolution, whichever occurs earlier. The type, incidence, timing (onset, duration), relationship, and severity of adverse events will be reported for treatment-emergent and serious adverse events. Reasons for withdrawal due to adverse events will also be reported. Narratives will be written for every adverse event classified as serious or associated with death.

Vital signs, ECGs and laboratory measurements will also be summarized descriptively.

